The proposed study builds on this successful NIDDK-funded pilot work to address the clear need for a men-tailored approach to diabetes prevention. *Power-Up* is an intervention that is: a) tailored to the needs and preferences of racial/ethnic minority men; b) delivered by men coaches in men-only groups; and c) uses adapted content that highlights issues relevant to men and messaging designed to be acceptable and engaging to men. Based on the pilot results, we propose to conduct a rigorous effectiveness evaluation using a pragmatic RCT design within diverse healthcare settings already implementing standard mixed-gender NDPP. The goals of this study are to: 1) test the effect of *Power-Up* on weight loss; 2) evaluate engagement of men in *Power-Up*; and 3) examine the reach, broader effectiveness, implementation, and costs of *Power-Up* to inform future dissemination efforts and plans for sustainability.

The proposed study will leverage existing collaborations with co-investigators testing best practices for recruitment, implementation and evaluation of NDPP in a bureau of the New York City Department of Health and Mental Hygiene. Through this partnership we will recruit 300 men from across a spectrum of primary care centers - from a major urban academic medical center to small- and medium-sized primary care practices throughout New York City serving disadvantaged communities. Electronic Health Record data will facilitate outreach to the population of eligible men, based on NDPP criteria, rather than relying on physician referral, and will establish a valid denominator for the total population of eligible men, allowing for a rigorous assessment of the reach of our recruitment approach and an evaluation of the representativeness of our sample. Indicators of effectiveness, adoption, implementation and cost will be analyzed, guided by the RE-AIM framework.

Aim 1. Assess the effect of *Power-Up* vs. NDPP on weight loss among racial/ethnic minority men at risk for diabetes.

Hypothesis 1 (Primary Outcome): Men randomized to *Power-Up* will achieve significantly greater weight loss at 16-weeks and 1-year than men in the standard care group referred to mixed-gender NDPP classes.

Aim 2. Compare engagement of racial/ethnic minority men at risk for diabetes in *Power-Up* vs. NDPP.

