Since there are likely to be 30,000-40,000 men patients across all of the PCIP/DOH and MMG practices who meet the eligibility criteria, we will be unable to call and screen all at once. Instead, we will target a small number of particular practices at a time, closing recruitment at these sites and moving on to other practices as we exhaust the full population of potentially eligible men at each site. We will also limit contact to those men who have had their weight measured within the last 6 months to limit the possibility that men will no longer be eligible for the programs based on weight and to increase the precision of our estimates for missing study-weights in the case of missing data or loss to follow-up. Our recruitment procedures represent a departure from current NDPP recruitment practices at PCIP/DOH and MMG practices, which rely on physicians to identify eligible patients and refer them to the NDPP. We expect that this active outreach approach will allow us to reach our recruitment goal of 300 enrolled participants given the large population of potentially eligible patients available through our health system partner. Given that we will not reach all practices in these networks, we will also be able to compare the reach and representativeness of our male sample across both arms of the trial, using EHR-based outreach, to that achieved by non-participating practices within our healthcare system partners' networks that continue to rely on physician referral for recruitment into NDPP.

RETENTION STRATEGIES. Our retention strategies are informed by our experience with the pilot and prior health behavior change and lifestyle intervention studies conducted by our team involving longitudinal follow-up of participants over 12 months or more. Based on this experience, we will provide monetary incentives for completion of telephone-administered surveys and for presenting for the collection of weights at the designated intervention session (e.g., 16 weeks and 12 months), which will be mailed to participants via the use of Clincards. We will also send reminders via text message, email, and/or mail for all first session, 16-week and 12 month weigh-ins, across both arms of the study. In addition, we will send cards in the mail to keep rapport by acknowledging birthdays and holidays and updating participants of the study. Participants will be supplied with scales to track their weight remotely.

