Development of study branding with a graphic designer to be used in all study communications and materials and sending periodic mailings to participants to remind them of upcoming appointments for surveys or weight-collection will also be helpful in fostering a sense of ongoing participation and helping participants keep their appointments. Bonding of participants within groups is one of the most important retention strategies promoted by the coaches. For example, buddy activities and raffle ticket giveaways during the class sessions have improved group cohesion and class retention in prior DPP efforts. Well-trained coaches who are cognizant of retention issues are likely the most effective strategy to reduce attrition. Coaches use texts and email in addition to phone calls to remind participants of upcoming sessions, address missed sessions and troubleshoot issues that come up regarding attendance. For example, when a participant misses a session, the coach will typically text and call the participant to make up the session via telephone and identify barriers to getting to session. Session scheduled times conflicting with work schedules and family commitments are the most common barriers identified. Thus, we have planned to hold sessions mostly in the evenings, with weekend sessions also available. Information from our baseline survey can also be used to help inform common reasons why a participant may miss sessions (e.g., childcare or complex work schedule). Participants will be contacted via text (with their permission) reminding them to complete study questionnaires, weigh-in prior to sessions, fill out their physical activity logs, and the link for joining the sessions.

PHS HUMAN SUBJECTS AND CLINICAL TRIALS STUDY

[figure not shown]
TIMELINE

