Study procedures will primarily take place in our study offices at AECOM and PCIP/NYC-DOHMH and at local sites of participating practices from the PCIP and MMG networks. Additional procedures for weight collection, when participants do not attend intervention sessions where weights are primarily measured, may take place at additional sites. Recruitment, eligibility screening, and enrollment procedures will be conducted by research assistants/prevention outreach specialists located at our AECOM and PCIP/NYC-DOH offices. Potentially eligible men will be: via telephone follow-up; informed of their risk for diabetes and the availability and efficacy of the DPP; evaluated for eligibility; asked to provide oral informed consent by phone; and then randomized to one of the two conditions. Random assignment will be conducted using envelopes with the randomization condition inside. The research coordinator will have access to the envelopes. Study coordinators will contact the research coordinator who will tell the SC which condition the participant will be receiving. Randomization will occur at AECOM for all participants. Random assignment, and final enrollment into the study will occur after telephone screening, and completion of baseline surveys. With leadership from [name] (Co-I), all

coach training for *Power-Up* intervention delivery will occur in AECOM or PCIP/NYC-DOHMH meeting space. NDPP training for coaches will occur through established programs.

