Potential participants who do not have capacity to provide consent will be provided with information about how to access the NDPP through talking with their provider who would discuss whether the program may or may not be appropriate for them. Potentially eligible subjects will be invited to participate, consented, randomized to a study arm and either directed to the *Power-Up* intervention coordinator or to the NDPP coordinator at PCIP depending on the patient's health care home. The consent document will include information about study procedures, including that participants will be randomized to either standard NDPP or *Power-Up*, that they will be contacted by telephone, email (if applicable) and mail for follow-up surveys, and the risks and benefits of the intervention. We will ask for permission to leave telephone messages, without identifying the exact purpose of the call, when we are making study-related calls. We will also ask for permission to send text messages via the coaches as reminders for sessions and questionnaires. Participation in the proposed study will be completely voluntary. Prospective subjects will be told that a decision to decline participation will not affect their health care.

The proposed research will follow the Health Insurance Portability and Accountability Act of 1996 (HIPAA) guidelines for protecting the privacy and documenting informed consent of participants. Intervention recruitment, consent, and enrollment will not begin until the study receives approval from the AECOM IRB, as outlined in the Consortium of Informed Consent Section.

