Adverse Event Monitoring. Participants who miss sessions will be contacted by their coach. If the coach is informed that the participant is hospitalized or deceased, the coach will report that information to AECOM or PCIP/NYC-DOHMH project manager immediately, who will in-turn report it to [name]. The two follow-up surveys (after completion of 16 Core sessions, and after completion of 6 maintenance sessions) also include questions about hospitalizations and other serious adverse events. These surveys will be administered primarily by telephone by our research staff based at our two sites and occasionally in person, when meeting participants to collect missing weights who have also been non-responsive to attempts to schedule a telephone survey, using equivalent procedures to those used for telephone administration. If, 1) the interviewer is informed of an adverse event in the course of the survey, or 2) while trying to reach the participant, the interviewer is informed by someone in the household of a subject's hospitalization or death, that event will be noted. Any hospital admission for a related condition or death from any cause will be immediately reported to [name] who will record them. The Einstein IRB will maintain reports of adverse events.

Information about adverse events will be sought as described above. Unanticipated (non-serious) adverse events will be reported to the IRB within 30 days of such an event using the AECOM IRB Adverse Event Report. Serious adverse events will be reported to the IRB within 48 hours by phone and email. A completed AECOM IRB Adverse Event Report will be submitted within 10 days of initial IRB notification. All deaths will be reported to the IRB within 48 hours of ascertainment. The monitor will maintain a file of all ascertained adverse events that can be used to submit summary reports.

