Early Termination. [name] and [name] will determine if the study is to be terminated prior to the scheduled study conclusion, in consultation with our DSMB. Early study termination will be considered in the event of a pattern of unanticipated serious adverse events determined to be possibly, probably or definitely related to the intervention or the data collection. In such a case, interim assessment would also be considered to ascertain if the events were associated with the intervention. In the absence of a pattern of unanticipated serious adverse events, given the minimal risk character of the intervention of this study, traditional statistical stopping rules for efficacy or safety of the intervention would not be applicable. However, early study termination will be considered if:

- subject recruitment falls below 20% of the projected number of subjects 6 months after the initiation of all stepped and potential recruitment strategies have been utilized, or
- if we fail to retain (as defined above) at least 70% of enrolled study subjects at any annual review.

[name] will consult with [name], come to agreement, seek consultation from the DSMB, and report a decision to terminate the study early to the IRBs within 48 hours of the determination and a narrative description of the reasons for early termination within 10 days.

Contact PD/PI: [name]

Overall Structure of the Study Team

The study team will be led by Drs. [name] and [name] (PIs), who are both based at Albert Einstein College of Medicine. Our AECOM study offices will house a project manager and two study coordinators who will have primary responsibility for conducting and overseeing all research activities related to participants recruitment and workshop. Drs. [name] and [name] (Co-Is) are also based at AECOM.

At PCIP/DOHMH [name] will oversee activities related to practice engagement, participant recruitment, assessment, and intervention delivery to participants recruited from PCIP-affiliated primary care practices. She will be supported by a full time onsite research assistant in our PCIP-based study office. She will coordinate regularly with the Einstein-based project manager and receive regular supervision from [name] to ensure consistency of procedures. Together, this team will provide input to the study plans and procedures from both Einstein and PCIP/DOHMH.

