All *Power-Up* coaches will be hired by the Einstein site. These coaches will be dedicated to deliver *Power-Up* PCIP-affiliated practices throughout New York City. The Einstein-based research staff will also coordinate their efforts with the research staff based at PCIP and provide support as needed.

All supplies and materials will be purchased by the Einstein site and delivered as needed to PCIP. All administration of PCIP-related expenses, outside of personnel costs for study staff, will also be carried out by our Einstein staff to maximize efficiency.

[name] will develop procedures for randomization of participants that via an electronic database that can be accessed by both sites and will develop a similar set of procedures and remotely accessible databases for data entry at each of the sites. All transmissions will be encrypted and delivered via secure servers.

[name] (PI) oversees a research lab at the Ferkauf Graduate School of Psychology, Yeshiva University, which is co-located with Einstein. Graduate students in the Clinical Health Psychology PhD program, as well as two post-doctoral fellows under his supervision, have relevant expertise and experience with qualitative interviewing, participant assessment, and data management/analysis. They will be involved in the activities of the proposed study, at PCIP, on an as-needed basis as part of their mentored research experience and training. All trainees who take part in the study will be trained in human subjects research and approved by the Einstein IRB prior to their involvement.

The organizational structure for the proposed project is based on a similar model that has proven effective for the *NYC Care Calls Study*, which enrolled 812 adults with type 2 diabetes from PCIP-affiliated practices. [name] (PI), Drs. [name] and [name] (Co-I) have a history of successful collaboration with [name] and PCIP on this project and this experience will ensure continued success in the proposed collaborative research.

The Dissemination Plan

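### Questionnaire text reminders and between-survey event detection run through the coaches, so either could differ by arm and by attendance; the study office should send the reminders, and event tables should show source

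*Protocol*

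**What the plan says.** **Questionnaire reminders.** Section 2a (Informed Consent) states: "We will also ask for permission to send text messages via the coaches as reminders for sessions and questionnaires". Retention Strategies mentions the same texts without naming a sender or an arm: "Participants will be contacted via text (with their permission) reminding them to complete study questionnaires". That section also makes a commitment that names both arms, but questionnaires are not on its list: "We will also send reminders via text message, email, and/or mail for all first session, 16-week and 12 month weigh-ins, across both arms".

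**Adverse events.** Adverse Event Monitoring, in the Data and Safety Monitoring Plan, opens with: "Participants who miss sessions will be contacted by their coach". A coach who learns of a hospitalisation or death reports it to a project manager. Both follow-up surveys also ask about hospitalisations and serious events, and interviewers note events that household members report while the interviewer is trying to reach a participant. Under Early Termination, if a pattern of related serious events appears, "interim assessment would also be considered to ascertain if the events were associated with the intervention".

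**The coaches.** Overall Structure of the Study Team says that all Power-Up "coaches will be hired by the Einstein site". For the comparator, the opening summary describes "diverse healthcare settings already implementing standard mixed-gender NDPP", and section 1b says "NDPP training for coaches will occur through established programs". The Protocol does not say who employs the NDPP coaches.

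**The concern.** A randomised comparison needs outcomes and events to be sought in the same way in both arms. Here two ascertainment steps are placed with the people who deliver the intervention, and those people differ by arm. No section gives NDPP coaches the same texting and event-reporting duties by name.

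Both steps also depend on class contact. The event route is triggered by a missed session and presupposes a coach who is following the man. Hypothesis 2 expects attendance to differ by arm, and section 1b plans EHR weights partly because some men will never attend. Section 2a itself treats attendance as a threat to validity: it rejects consent at the first session because that would artificially equate the arms on attending it.

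Two things are at stake. The follow-up questionnaires carry the patient-reported outcomes of Aim 3, so unequal response could bias those comparisons. The event counts feed the DSMB summary tables and any interim assessment under Early Termination, so unequal detection could blur whether events are associated with the intervention.

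**Working it through.** No figure in the Protocol is disputed and no calculation applies. The check is to set the relevant sections side by side.

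| Step | Who does it | Stated to be the same in both arms? |
|---|---|---|
| First-session and weigh-in reminders (Retention Strategies) | The study | Yes, explicitly |
| Questionnaire texts (section 2a) | The coaches | Not stated |
| Questionnaire texts (Retention Strategies) | Sender not named | Not stated |
| Telephone, email and mail contact for surveys (section 2a) | Sender not named | No difference stated |
| Mailed reminders and survey incentives (Retention Strategies) | The study | No difference stated |
| Administering the surveys (section 1b; Adverse Event Monitoring) | Research staff | No difference stated |
| Event detection between surveys (Adverse Event Monitoring) | Mainly the coach, after a missed session | Not stated |
| Event questions in the surveys; household reports (Adverse Event Monitoring) | Research staff | No difference stated |

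**Are the coaches arm-specific?** In Power-Up, yes: they are study hires. In NDPP it is an inference. Control men are referred to classes in settings that already run NDPP, and the NDPP coaches are trained through established programmes. Programme employment is the natural reading, but it is not written down.

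**Which way would event detection be biased?** Two mechanisms pull in opposite directions.
1. Study-hired coaches may follow up and report more diligently than programme staff. That would raise detection in Power-Up.
2. The coach's contact is triggered by a missed session. If Hypothesis 2 holds, control men who have joined a class miss more sessions and trigger more contacts. That would raise detection in NDPP. A control man who never joins a class may, on the other hand, have no coach to contact him at all.

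The net direction is therefore unknown.

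**How large could it be?** The Protocol gives no survey response rate, no probability that a coach learns of an event, and no event rate. Any ratio of captured events, or any shift in a patient-reported score, would only restate the rates assumed for it, so none is offered here.

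**Where would a difference remain?** A man who answers the next survey can report a hospitalisation that no coach heard of. What is left is mainly events in survey non-responders that household contact also misses, and the timing of detection before the next survey.

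**Does it reach the primary outcome?** No. Weight comes from connected scales and EHR records, and the weigh-in reminders are promised in both arms.

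**The case against.** The strongest reply is that the surveys do not run through the coaches. The sentence in section 2a asks permission for one added channel. The same section provides for telephone, email and mail contact for the follow-up surveys. Research staff administer them, sometimes in person to reach non-responders, and completion is paid. A text from a coach is a marginal addition. This stands, and it limits the effect on survey response.

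Second, the asymmetry is not stated. The coach duties are written without naming an arm, coaches may report to the project manager at either study office, and the study team supervises control-arm weight and attendance collection. This also stands: a reader might infer that NDPP coaches will not send the texts or report events, but the Protocol does not say so. Nor does it say that they will, and it uses explicit both-arms wording for the weigh-in reminders, where the point was settled.

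Third, a reader might infer that more contact in Power-Up will make that arm look more harmful. The documents do not support this, because the missed-session trigger could push detection the other way.

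Fourth, Early Termination is not a plain comparison of counts. It is prompted by a pattern of serious events judged related, after which an interim assessment is considered, and the DSMB may request any analysis. This lowers the stakes, but an assessment of association would still rest on events found by routes that may differ by arm.

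**Conclusion.** The point holds as a modest weakness in a stated procedure. Questionnaire texts and the main route to events between surveys are placed with intervention staff who are study hires in one arm and, by inference, programme staff in the other. Survey response and between-survey event detection could therefore differ by arm and by attendance. Neither the direction nor the size can be derived from the Protocol.

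The conclusion rests on one assumption: that NDPP coaches do not in practice carry the same texting and reporting duties in the same way. If they do, the difference by employer disappears, but the dependence on attendance remains.

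The reach is limited. The patient-reported outcomes are exploratory, staff-run surveys and household reports recover many of the events that coaches could miss, and the primary weight outcome is untouched. A reader might also infer that the between-arm event assessment should use survey-reported events only. That does not follow: men who die cannot answer a survey and men in hospital may not, so such a rule would remove deaths and some serious events from the comparison.

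**What to change.** 1. In section 2a, have the study office send the questionnaire reminders, with the same text and timing in both arms, as Retention Strategies already does for weigh-ins. Limit coach texts to sessions, and name the study office as sender in the matching sentence of Retention Strategies.
2. In the event summary tables for the DSMB, show events by arm and by source: coach report, survey, household contact.
3. State that any assessment under Early Termination uses all events. The source column then lets it separate events found on the common survey schedule, including household reports made during survey attempts, from those reported by coaches. Individual reporting of every event is unchanged.

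The cost is Protocol wording, one more column in the event tables, and study staff sending some texts that coaches would otherwise have sent. The reminder channel already exists.
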